8.4.2. Method of Detecting AEs and SAEs

Care will be taken not to introduce bias when detecting AEs and/or SAEs. Open-ended and non-leading verbal questioning of the participant is the preferred method to inquire about AE occurrences.

8.4.3. Follow-up of AEs and SAEs

Adverse events resulting in study termination will be followed to the satisfactory resolution and determination of outcome as ascertained by the investigator.

After the initial AE/SAE report, the investigator is required to proactively follow each participant at subsequent visits/contacts. All SAEs will be followed until resolution, stabilization, the event is otherwise explained, or the participant is lost to follow-up (as defined in [Section 7.3](#)). Further information on follow-up procedures is provided in [Appendix 4](#).

8.4.4. Regulatory Reporting Requirements for SAEs

- Prompt notification by the investigator to the sponsor of an SAE is essential so that legal obligations and ethical responsibilities towards the safety of participants and the safety of a study intervention under clinical investigation are met.
- The sponsor has a legal responsibility to notify both the local regulatory authority and other regulatory agencies about the safety of a study intervention under clinical investigation. The sponsor will comply with country-specific regulatory requirements relating to safety reporting to the regulatory authority, IRB/IEC, and investigators.
- An investigator who receives an investigator safety report describing an SAE or other specific safety information (eg, summary or listing of SAEs) from the sponsor will review and then file it and will notify the IRB/IEC, if appropriate according to local requirements.

- Investigator safety reports will be prepared for SUSARs according to local regulatory requirements and sponsor policy and forwarded to investigators as necessary. The RSI for the determination of expectedness of lurbinectedin can be found in the IB ([Pharma Mar IB, 2022](#)).

8.4.5. Pregnancy

- Details of all pregnancies in female participants and female partners of male participants will be collected after the start of study intervention and until 30 days of the last dosing of the study participant.
- If a pregnancy is reported during treatment or within 30 days after the last dose of IP, the investigator will record pregnancy information on the appropriate form and submit it to the sponsor within 24 hours of learning of the female participant or female partner of male participant (after obtaining the necessary signed informed consent from the female partner) pregnancy.
- While pregnancy itself is not considered to be an AE or SAE, any pregnancy complication or elective termination of a pregnancy for medical reasons will be reported as an AE or SAE.
- Abnormal pregnancy outcomes (eg, spontaneous abortion, fetal death, stillbirth, congenital anomalies, ectopic pregnancy) are considered SAEs and will be reported as such.
- The participant/pregnant female partner will be followed to determine the outcome of the pregnancy. The investigator will collect follow-up information on the participant/pregnant female partner and the neonate, and the information will be forwarded to the sponsor.
- Any post-study pregnancy-related SAE considered reasonably related to the study intervention by the investigator will be reported to the sponsor as described in [Section 8.4.4](#). While the investigator is not obligated to actively seek this information in former study participants/pregnant female partner, he or she may learn of an SAE through spontaneous reporting.
- Any female participant who becomes pregnant while participating in the study will discontinue study intervention.

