2.3.1. Risk Assessment

Potential risks to participants in this study are anticipated to be consistent with the known pharmacology and safety profile of lurbinectedin in previous clinical studies, as described in the lurbinectedin IB (Pharma Mar IB, 2022). The main risks associated with lurbinectedin are AEs related to reversible myelosuppression. There is also a risk of hepatotoxicity and gastrointestinal toxicity (specifically nausea and vomiting). Episodes of rhabdomyolysis were reported in 2 patients treated with single-agent lurbinectedin, although none of them occurred at the recommended dose of 3.2 mg/m² Q3W. A small number of reports of rhabdomyolysis have been received in the postmarketing setting. Based on animal studies and its mechanism of action, lurbinectedin may cause embryo-fetal toxicity, and effective methods of contraception are recommended to be used by study participants.

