- b. Has a pre-identified germline and/or somatic pathogenic mutation (a mutation that significantly affects the functions of genes associated with oncogenesis [NCI, 2022]) in one of the following genes: *BRCA1/2*, *PALB2*, *RAD51/51B/51C/51D*, *ATR*, *ATM*, *ARID1A*, *BAP1*, *CHEK2*, *RAD50*, *RAD54*.
 - c. Received at least 1 prior line of therapy.
 - d. Patients who have received prior PARPi are allowed **unless** they progressed within ≤ 3 months after the first dose with PARPi

Informed Consent

4. Is capable of giving signed informed consent as described in [Section 10.1.3](#), which includes compliance with the requirements and restrictions listed in the ICF and in this protocol.

Age

5. Is ≥ 18 years of age at the time of signing the informed consent.

Safety Parameters

6. Has ECOG performance status of 0 or 1.
7. Has a life expectancy of ≥ 3 months.
8. Has adequate bone marrow function, as follows:
 - a. ANC $\geq 1500/\text{mm}^3$ or $\geq 1.5 \times 10^9/\text{L}$,
 - b. Platelets $\geq 100,000/\text{mm}^3$ or $\geq 100 \times 10^9/\text{L}$,
 - c. Hemoglobin ≥ 9 g/dL (note: may have been transfused).
9. Has as adequate renal function, defined as estimated creatinine clearance ≥ 30 mL/min as calculated using the Cockcroft-Gault equation or by 24-hour urine collection for creatinine clearance or according to the local institutional standard method.
10. Has adequate liver function, as follows:
 - a. Total serum bilirubin $\leq 1.5 \times \text{ULN}$,
 - b. Aspartate aminotransferase and alanine aminotransferase $\leq 3 \times \text{ULN}$, or for participants with documented metastatic liver disease, AST and ALT levels $\leq 5 \times \text{ULN}$.

Tumor Assessment requirement

11. Has measurable disease in accordance with RECIST v1.1.

Sex and Contraceptive/Barrier Requirements

12. Male and female
 - a. **Male participants:**

Male participants are eligible to participate if they agree to the following during the study intervention period and for at least 4 months after the last dose of study intervention:

- Refrain from donating sperm.
PLUS, either:
- Be abstinent from heterosexual intercourse as their preferred and usual lifestyle (abstinent on a long-term and persistent basis) and agree to remain abstinent.
OR
- Must agree to use contraception/barrier as detailed below.

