 - Agree to use a male condom [with female partner use of an additional highly effective contraceptive method with a failure rate of < 1% per year as described in [Appendix 5 Contraceptive and Barrier Requirements](#)] when having sexual intercourse with a woman of childbearing potential who is not currently pregnant. Note: male participants who are azoospermic (vasectomized or due to a medical cause) are still required to follow the protocol-specified contraception/barrier criteria.

b. Female participants:

- A female participant is eligible to participate if she is not pregnant or breastfeeding, and one of the following conditions applies:
 - Is a woman of non-childbearing potential as defined in [Appendix 5 Contraception and Barrier Guidance](#).
OR
 - Is a WOCBP and using a contraceptive method that is highly effective (with a failure rate of < 1% per year), preferably with low user dependency, as described in [Appendix 5 Contraception and Barrier Guidance](#) during the study intervention period and for at least 6 months after the last dose of study intervention and agrees not to donate eggs (ova, oocytes) for the purpose of reproduction during this period. The investigator should evaluate the potential for contraceptive method failure (eg, noncompliance, recently initiated) in relationship to the first dose of study intervention.
- A WOCBP must have a negative highly sensitive pregnancy test (urine or serum, as required by local regulations) within 7 days before the first dose of study intervention, see [Section 8.3.6: Pregnancy Testing](#).
 - If a urine test cannot be confirmed as negative (eg, an ambiguous result), a serum pregnancy test is required. In such cases, the participant must be excluded from participation if the serum pregnancy result is positive.
- Additional requirements for pregnancy testing during and after study intervention are located in [Section 8.3.6 Pregnancy Testing](#).
- The investigator is responsible for review of medical history, menstrual history, and recent sexual activity to decrease the risk for inclusion of a woman with an early undetected pregnancy.

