8.3.6. Pregnancy Testing

- Refer to Section 5.1 Inclusion Criteria for pregnancy testing entry criteria.
- Pregnancy testing (urine or serum as required by local regulations) should be conducted according to the SoA (Table 3).
- Pregnancy testing (urine or serum as required by local regulations) should be repeated 30 days after last dose of lurbinectedin.
- Additional serum or urine pregnancy tests may be performed, as determined necessary by the investigator or required by local regulation, to establish the absence of pregnancy at any time during the participant's participation in the study.

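### Pregnancy collection stops 30 days after the last dose, while contraception is required for at least 4 or 6 months; after day 30 only related SAEs that happen to come to notice are reportable

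*Protocol*

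**What the plan says.** Four parts of the protocol bear on this.

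- **Collection and reporting (Section 8.4.5).** The section covers pregnancies in women on the study and in the partners of men on the study. Their details, it says, "will be collected after the start of study intervention and until 30 days of the last dosing of the study participant". The form due within 24 hours is conditional: "If a pregnancy is reported during treatment or within 30 days after the last dose of IP". The same section states "While pregnancy itself is not considered to be an AE or SAE". It classes abnormal outcomes such as fetal death or congenital anomaly as SAEs. It also lets a related pregnancy SAE arising after the study be reported, but the investigator has no duty to look for one.
- **Contraception (Section 5.1).** Men must follow the requirements "during the study intervention period and for at least 4 months after the last dose of study intervention". Women of childbearing potential must use a highly effective method "during the study intervention period and for at least 6 months after the last dose of study intervention".
- **Reason (Section 2.3.1).** From animal data and mechanism of action, "lurbinectedin may cause embryo-fetal toxicity, and effective methods of contraception are recommended to be used by study participants".
- **Testing (Section 8.3.6).** After treatment the pregnancy test "should be repeated 30 days after last dose of lurbinectedin". Later tests are left to the investigator or to local regulation.

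**The concern.** The protocol asks participants to prevent pregnancy for months after the last dose because the drug may harm a fetus. It stops asking whether pregnancy occurred after 30 days, and it gives no reason for the difference. If contraception fails in the remaining months, the sponsor may never hear of the pregnancy.

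What is at stake is safety information, not efficacy. If only related adverse outcomes that someone happens to notice can surface, the sponsor also lacks a count of the pregnancies from which they came, and any such case is hard to interpret.

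**Working it through.** The documents state no figure to reproduce, so the check compares the periods and then the reporting routes.

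**Inputs**
- Pregnancy collection after the last dose: 30 days (Protocol 8.4.5).
- Minimum contraception after the last dose: 4 months for men, 6 months for women of childbearing potential (Protocol 5.1).
- Days per month: 30.4375 (the conversion in SAP Section 8.5).

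**Formula:** uncovered days = months × 30.4375 − 30; uncovered share = uncovered days ÷ (months × 30.4375).

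| | Contraception period (days) | Uncovered days | Share |
|---|---|---|---|
| Men | 4 × 30.4375 = 121.75 | 121.75 − 30 = 91.75 | 91.75 ÷ 121.75 = 75% |
| Women | 6 × 30.4375 = 182.6 | 182.6 − 30 = 152.6 | 152.6 ÷ 182.6 = 84% |

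Both contraception periods are stated as minimums, so the uncovered days are minimums too. The shares are of calendar time, not of expected pregnancies.

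**What can be reported after day 30**
1. Routine AE and SAE collection ends at the EOT or early discontinuation visit (Section 8.4.1).
2. During survival follow-up, only treatment-related SAEs that are volunteered are recorded (Section 8.4.1).
3. After the study, a pregnancy-related SAE is reported if the investigator learns of it and judges it reasonably related (Sections 8.4.1 and 8.4.5).
4. Pregnancy itself is neither an AE nor an SAE, so a pregnancy without such an SAE meets none of these conditions.

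**The edge of the window.** The 24-hour trigger depends on when the pregnancy is reported, not on when it began. The EOT visit is due 30 ± 7 days after the last dose (Section 7.1), that is, on days 23 to 37. If the final pregnancy test is done at a visit on days 31 to 37, which is within the permitted window, a positive result already falls outside the trigger. So does a pregnancy conceived on treatment and first mentioned on, say, day 40.

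**Contacts already planned.** Survival calls follow every 3 months after EOT. With EOT on day 30, the first falls near day 30 + 91.3 = 121 and the second near day 30 + 182.6 = 213. The first is close to the end of the men's 4 months (day 122), and the second comes after the women's 6 months (day 183).

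**The case against.** The best case for the plan has four parts.

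- **Serious outcomes are not lost by rule.** Abnormal outcomes are SAEs under Section 8.4.5, congenital anomaly is an SAE criterion in Appendix 4, and related SAEs remain reportable after discharge from the study. Pregnancies reported inside the window are followed to outcome, with information on the neonate. A reader might infer that all later pregnancies go unreported, or that the safety database could never show their outcomes. The documents do not support that. What stands is narrower: the later routes are passive, need a relatedness judgement and miss a pregnancy without an SAE.
- **The contraception period is not called an exposure period.** A reader might infer that every pregnancy in months 2 to 6 is drug-exposed. Section 2.3.1 gives a reason for contraception but no duration, and the 4 and 6 months may include a precautionary margin. For partners of male participants the stated minimum also ends at month 4. This objection stands, so the gap should be described as lying within the contraception period.
- **The two rules can both be followed.** Thirty days matches the TEAE period, the repeat pregnancy test and the nominal EOT visit, and data collection serves a different purpose from contraception. A reader might call this a contradiction, but it is an unexplained difference between windows. The difference still has the consequence shown above.
- **Events will be few.** Participants have pretreated advanced cancer and contraception is mandatory. This limits the weight of the point without removing it, because each rare case carries more information.

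**Conclusion.** The concern holds in a limited form. As written, about 92 of 122 days (75%) for men and 153 of 183 days (84%) for women of the minimum contraception period after the last dose have no active pregnancy collection. In that time a pregnancy can enter the safety record only through an SAE that the investigator happens to learn of and considers related. Because the trigger is tied to the report date, some pregnancies that began on treatment are missed as well.

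The conclusion rests on reading Sections 5.1, 8.3.6, 8.4.1 and 8.4.5 together, and on a month of 30.4375 days. It assumes nothing about how long a pregnancy would be exposed to drug, and it takes no view on which contraception period is right. The documents give no expected number of pregnancies. ORR, the other efficacy endpoints and the cohort decisions do not depend on this point. It is a worthwhile, low-cost safety improvement.

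**What to change.** Reconcile Section 8.4.5, and the test timing in Section 8.3.6, with Section 5.1:

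- Collect, report and follow any pregnancy that begins while the protocol still requires contraception, for female participants and for partners of male participants.
- Base the reporting trigger on when the pregnancy began, with the 24-hour clock running from when the site learns of it.
- Add a pregnancy question to the first two 3-monthly survival calls. Name another contact route for cohorts closed for futility, because Section 4.1 ends survival follow-up there.
- If 30 days is deliberate, state the reason in Section 8.4.5 instead.

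The change affects data collection only; dosing, treatment and the contraception requirement stay as they are. It costs a protocol amendment with ethics committee approval, one added question, a contact arrangement for closed cohorts, and signed consent from partners for partner pregnancies, which Section 8.4.5 already requires.

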8.4.6. Disease-Related Events and/or Disease-Related Outcomes Not Qualifying as AEs or SAEs

The following DREs are common in participants with advanced or metastatic solid tumors:

- Disease progression
- Death

Because these events are typically associated with the disease under study, they will not be reported according to the standard process for expedited reporting of SAEs even though the

event may meet the definition of an SAE. These DREs will be monitored by a medical monitor on a routine basis.

NOTE: However, if the following condition applies, then the event must be recorded and reported as an AE/SAE (instead of a DRE):

The investigator considers that there is a reasonable possibility that the event was related to study intervention.

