8.4.1. Time Period and Frequency for Collecting AE and SAE Information

All AEs and SAEs will be collected from the start of intervention until the EOT or E/D visit as specified in the SoA (Table 3) and per Section 8.4.3. Participants' discontinuation from study treatment with an ongoing treatment-related AE should be followed until satisfactory resolution per the investigator. Any spontaneous reporting of treatment-related SAE during the OS follow-up will be also collected and reported.

Note: All SAEs that occur after the consent form is signed but before study intervention/treatment must be reported by the investigator if they cause the participant to be

excluded from the trial, or are the result of a protocol-specified intervention, including but not limited to diet, placebo treatment, or a procedure.

Medical occurrences that begin before the start of study intervention but after obtaining informed consent will be recorded as Medical History/Current Medical Conditions, not as AEs.

All SAEs will be recorded and reported to the sponsor or designee immediately and within 24 hours of first knowledge of the event by study personnel, as indicated in [Appendix 4](#). The investigator will submit any updated SAE data to the sponsor within 24 hours of it being available. All treatment-related deaths will be reported as SAEs. Deaths due to progression of disease are not SAEs and should not be reported as SAEs.

Investigators are not obligated to actively seek information on new AEs or SAEs after conclusion of the study participation. However, if the investigator learns of any SAE, including a death, at any time after a participant has been discharged from the study, and he/she considers the event to be reasonably related to the study intervention or study participation, the investigator should promptly notify the sponsor.

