If an event is not an AE per definition above, then it cannot be an SAE even if serious conditions are met (eg, hospitalization for signs/symptoms of the disease under study, death due to progression of disease).

An SAE is defined as any untoward medical occurrence that, at any dose:
Results in death

Is life-threatening
 
 The term ‘life-threatening’ in the definition of ‘serious’ refers to an event in which the participant was at risk of death at the time of the event. It does not refer to an event, which hypothetically might have caused death, if it were more severe.

Requires inpatient hospitalization or prolongation of existing hospitalization
 
 In general, hospitalization signifies that the participant has been admitted (usually involving at least an overnight stay) at the hospital or emergency ward for observation and/or treatment that would not have been appropriate in the physician’s office or outpatient setting. Complications that occur during hospitalization are AEs. If a complication prolongs hospitalization or fulfills any other serious criteria, the event is serious. When in doubt as to whether “hospitalization” occurred or was necessary, the AE should be considered serious. Hospitalization for elective treatment of a pre-existing condition that did not worsen from baseline is not considered an AE.

Results in persistent or significant disability/incapacity
 
 The term disability means a substantial disruption of a person’s ability to conduct normal life functions. This definition is not intended to include experiences of relatively minor medical significance such as uncomplicated headache, nausea, vomiting, diarrhea, influenza, and accidental trauma (e.g., sprained ankle) that may interfere with or prevent everyday life functions but do not constitute a substantial disruption.
Is a congenital anomaly/birth defect

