#### **10.2.7. Overall Summary of Adverse Events**

A general summary of AEs will be provided with the number and percentage of participants in the Safety analysis set who experienced the following types of events across the cohorts:

- Participants with any TEAE
- Participants with any Treatment-Related TEAE
- Participants with TEAE by Worst CTCAE Grade

Jazz Pharmaceuticals, Inc.

JZP712-201 Statistical Analysis Plan - Protocol Amendment

2

- Participants with any TEAE CTCAE Grade  $\geq 3$
- Participants with any Serious TEAE
- Participants with any Serious Treatment-Related TEAE
- Participants with any TEAE Leading to Death
- Participants with any TEAE Leading to Study Treatment Discontinuation
- Participants with any Treatment-Related TEAE Leading to Study Treatment Discontinuation
- Participants with any TEAE Leading to Study Treatment Reduction/Delay/Interruption
- Participants with any Treatment-related TEAE Leading to Study Treatment Reduction/Delay/Interruption

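### Protocol 8.4.6 exempts death of any cause from expedited SAE reporting, while 8.4.1 and Appendix 4 exempt death due to progression, so a death that is neither due to progression nor judged related falls under opposite instructions

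*Protocol*

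**What the plan says.** Protocol Section 8.4.6 names two DREs that are common in this population: disease progression and, as a separate bullet, death. The reason given is "Because these events are typically associated with the disease under study", and the consequence is that "they will not be reported according to the standard process for expedited reporting of SAEs". The sentence goes on to say that this applies even where the event may meet the SAE definition. A medical monitor follows DREs routinely, and no time limit is stated. There is one exception, "The investigator considers that there is a reasonable possibility that the event was related to study intervention", and "then the event must be recorded and reported as an AE/SAE (instead of a DRE").

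Section 8.4.1 is narrower: "Deaths due to progression of disease are not SAEs and should not be reported as SAEs". It also makes every treatment-related death an SAE and puts all SAEs on a 24-hour clock.

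Appendix 4, under the definition of an SAE, makes any untoward medical occurrence that results in death an SAE. Its examples of what falls outside are "hospitalization for signs/symptoms of the disease under study, death due to progression of disease". Its reporting section repeats the 24-hour requirement.

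On analysis, Protocol 9.4.4.1 tabulates Grade 5 TEAEs and also summarizes and lists all deaths. SAP 10.2.7 counts "Participants with any TEAE Leading to Death". SAP 10.2.5 summarizes all deaths, and separately those within 30 days of the last dose, in each case with reasons.

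**The concern.** Progression has its own bullet in 8.4.6, so the death bullet is not merely a restatement of it. Read literally, it covers a death from any cause unless the investigator judges it related. Consider a participant who dies of an infection or a cardiac event that is neither progression nor considered related. Under 8.4.1 and Appendix 4 this is an SAE due within 24 hours. Under 8.4.6 it is a DRE for routine monitoring.

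Timely notice matters here. The protocol's design table gives the data monitoring committee as not applicable, and closing a cohort for safety rests on the sponsor's ongoing review (Sections 4.1 and 10.1.5). Section 2.3.1 names reversible myelosuppression as the main risk, so a fatal infection is an event whose causality may be hard to judge. Appendix 4 asks for facts, evidence or arguments that suggest a causal relationship before one is called a reasonable possibility. An ambiguous infectious death could therefore be called unrelated in good faith, and for such a death the two sets of instructions diverge.

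**Working it through.** No arithmetic applies. The check is to sort deaths into three types and read each section against each type.

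| Type of death | 8.4.6 | 8.4.1 | Appendix 4 |
|---|---|---|---|
| Due to progression, not judged related | DRE, no expedited report | Not an SAE | Not an SAE |
| Judged related to treatment | AE/SAE, not a DRE | SAE, 24 hours | SAE, 24 hours |
| Neither due to progression nor judged related | DRE, no expedited report | Not exempted; SAE, 24 hours | Fatal untoward event: SAE, 24 hours |

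The sections agree on the first two rows. The conflict is confined to the third, which includes deaths of unknown cause that are judged unrelated.

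Does one section settle the third row?

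1. Appendix 4 does not, because 8.4.6 says that its exemption applies even to events that may meet the SAE definition. Pointing to the definition leaves the conflict in place.
2. Section 8.4.1 does not settle it expressly. It speaks of related deaths and of progression deaths. It reaches the third type only through its general rule that all SAEs are reported within 24 hours, whereas 8.4.6 names death outright.
3. The heading of 8.4.6 suggests that disease-related deaths were meant. But the stated reason is that such events are typically associated with the disease, and nothing requires the individual death to be due to it.

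Next, the route from reporting to the tables. The exempted item is the outcome, death. A fatal infection or cardiac event is not on the DRE list. Section 8.4.1 still has all AEs collected, and Appendix 4 has the diagnosis recorded where possible and graded, with Grade 5 for a death related to an AE. If the site does this, the event enters the Grade 5 tables in Protocol 9.4.4.1 and SAP 10.2.1 and the fatal-TEAE count in SAP 10.2.7. It is missing from those counts only if the site records the DRE and nothing else. The title of 8.4.6, which describes its events as not qualifying as AEs or SAEs, and its wording that a related event becomes an AE/SAE in place of a DRE, make that a foreseeable reading. In either case the death stays in the summaries in Protocol 9.4.4.1 and SAP 10.2.5.

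**The case against.** The strongest reply is that the protocol still requires the report. Section 8.4.1 and Appendix 4 both set the 24-hour clock for all SAEs, and an event would be missed only if a site followed 8.4.6 over both. The underlying diagnosis must still be collected as an AE. There are other safeguards: Section 8 asks for immediate safety concerns to be discussed with the sponsor at once, Section 10.1.5 has the sponsor assess safety continuously, and a medical monitor follows DREs. The Appendix 4 exclusion is also introduced as examples, and that appendix separately excludes expected signs and symptoms of the disease, so it is not strictly limited to progression deaths.

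Most of this stands, and it limits the consequences. A reader might infer that these deaths do escape 24-hour reporting, that they do drop out of the Grade 5 counts, or that the investigator's causality judgement alone decides whether the sponsor learns of them. The documents support none of these as fact: the 24-hour rule remains in two other places, no text removes DREs from the TEAE tables, and other routes to the sponsor exist.

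The reply does not remove the conflict. Two instructions for the same death cannot both be followed. Routine monitoring and end-of-study death tables do not replace a 24-hour notice.

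**Conclusion.** The inconsistency is real and narrow. For one of the three types of death, neither due to progression nor judged related, 8.4.6 gives the opposite instruction to 8.4.1 and Appendix 4. Late or missing expedited reports are possible, and so is under-counting among Grade 5 TEAEs and TEAEs leading to death. The first depends on a site following 8.4.6, the second on its also recording only the DRE. All-deaths summaries are unaffected.

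The number of events cannot be derived from the documents. They do not say what share of deaths would be neither progression nor judged related, or how sites would resolve the conflict. A count per cohort would only restate assumptions on both, so none is given. The finding rests on the text alone and needs no such figure. It merits correction because the safety decisions depend on sponsor review without a monitoring committee and the change is small.

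**What to change.** In Protocol 8.4.6, change the second bullet from death to death due to progression of the disease under study, so that it matches 8.4.1 and the example in Appendix 4. Add one sentence stating that other fatal events follow the standard AE/SAE recording and 24-hour reporting in 8.4.1 and Appendix 4 regardless of causality. Nothing further is needed to reconcile the sections. In particular, a new rule that every other death must be entered as a Grade 5 AE would go beyond reconciliation and could clash with the Appendix 4 exclusion of expected disease signs and symptoms.

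The cost is a short change in the next amendment, a note to sites, and a few more SAE reports. No endpoint, sample size or SAP table changes.
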